3.2 Participant Grouping

There are two treatment classes for the LTE and Integrated Analyses:

- **Group T-T** includes participants who were exposed to AL002 during the Core Study. They will continue at their Core Study AL002 dosage during the LTE Study if enrolled in the LTE Study. Group T-T is further broken down as AL002 15 mg/kg, 40 mg/kg, and 60 mg/kg treatment groups.

- **Group P-TC** includes participants who were exposed only to placebo during the Core Study. They will be assigned to the TC during the LTE Study if enrolled in the LTE Study. Group P-TC might be separated into placebo and TC treatment groups depending on the summaries/analyses.

For Group P-TC, the data collected when the participants were receiving placebo in the Core Study might be summarized and/or analyzed separately from the data collected once the participants received the first study drug administration in the LTE Study. The data collected when the participants were receiving placebo in the Core Study up to the day before the participants received the first study drug administration in the LTE Study (separately from the data collected in the LTE Study) is referred to as **the Placebo Data** throughout the SAP. And it includes the data from the placebo participants who did not enroll in the LTE Study. The data collected on or after the day when the participants received the first study drug administration in the LTE Study is referred to as **the TC Data** throughout the SAP.

The first dose date of AL002 refers to the earliest date of any amount of AL002 administered across the Core Study and the LTE Study. **The last dose date of AL002** refers to the latest date of any amount of AL002 administered across the Core Study and the LTE Study. **The first dose date of any study drug** refers to the earliest date of any study drug administered, including placebo, across the Core Study and the LTE Study.

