|----------------|------------|---------------------------|--|
| Week 132 | 925 | [912, 939] | |
| Week 136 | 953 | [940, 967] | |
| Week 140 | 981 | [968, 995] | |
| Week 144 | 1009 | [996, 1023] | |
| Week 148 | 1037 | [1024, 1065] | |
| Week 156 | 1093 | > 1065 | |

^a Target Day and Core Study Day are based on Core Study Day 1.

^b LTE Day 1 represents Core Study Day of date of LTE Study Day 1. If no such date, use Core study day of the last visit date among Core visits and LTE screening visit.

Table 7-2. Analysis Visit Windows for C-SSRS Assessments Based on LTE Study Day^a

| Analysis Visit | Target Day | Analysis Visit Window |
|----------------|------------|-----------------------|
| LTE Baseline | 1 | ≤ 1 |
| LTE Week 4 | 29 | [2, 43] |
| LTE Week 8 | 57 | [43, 71] |
| LTE Week 12 | 85 | [72, 99] |
| LTE Week 16 | 113 | [100, 127] |
| LTE Week 20 | 141 | [128, 155] |
| LTE Week 24 | 169 | [156, 183] |
| LTE Week 28 | 197 | [184, 211] |
| LTE Week 32 | 225 | [212, 239] |
| LTE Week 36 | 253 | [240, 267] |
| LTE Week 40 | 281 | [268, 295] |
| LTE Week 44 | 309 | [296, 323] |
| LTE Week 48 | 337 | [324, 365] |
| LTE Week 56 | 393 | > 365 |

^a Target Day and LTE Study Day are based on LTE Study Day 1, unless indicated otherwise.

Table 7-3. Analysis Visit Windows for Hematology, Chemistry and Urinalysis Assessments Based on Core Study Day^a

| Analysis Visit | | Target Day | T-T Analysis Visit Window | Placebo Analysis Visit Window ^b |
|--|--------------------------|------------|---------------------------|--|
| Core Baseline | | - | ≤ 1 | ≤ 1 |
| Week 2 | | 15 | [2, 22] | [2, 22] |
| Week 4 | | 29 | [23, 36] | [23, 36] |
| Week 6 | | 43 | [37, 64] | [37, 64] |
| Week 12 (Hematology and Chemistry only) | | 85 | [65, 141] | [65, 141] |
| Week 28 | Hematology and Chemistry | 197 | [142, 239] | [142, 239] |
| | Urinalysis | | [65, 323] | [65, 323] |
| Week 40 (Hematology and Chemistry only) | | 281 | [240, 323] | [240, min (323, LTE Day 1)] |
| Week 52 | | 365 | [324, 463] | [324, min (463, LTE Day 1)] |
| Week 80 | | 561 | [464, 617] | [464, min (617, LTE Day 1)] |
| Week 96 | | 673 | [618, 687] | [618, min (687, LTE Day 1)] |
| Week 100 | | 701 | [688, 743] | [688, LTE Day 1] |
| Week 112 (Hematology and Chemistry only) | | 785 | [744, 841] | |
| Week 128 | Hematology and Chemistry | 897 | [842, 939] | |
| | Urinalysis | | [744, 1037] | |
| Week 140 (Hematology and Chemistry only) | | 981 | [940, 1037] | |
| Week 156 | | 1093 | > 1037 | |

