7.4 Safety Analyses

All safety endpoints will be summarized with the Integrated Analysis, unless otherwise specified. The selected safety endpoints that will be summarized with the LTE Analysis are specified in the respective sections.

All LTE Analysis for a safety endpoint will be based on the ATS-LTE, unless otherwise specified. All Integrated Analysis for a safety endpoint will be based on the Non-e4/e4 Set, unless otherwise specified. Analysis sets are defined in Section 5.

Analyses (including analysis sets that analyses will be conducted on) to be performed for each interim analysis (IA) are specified in Section 8.

Unless otherwise specified, CFB for Group T-T and placebo will be based on the Core baseline. CFB for Titration Cohort will be based on the LTE baseline. Baseline is defined in Section 6.1. Core baseline and LTE baseline are referred to as baseline for simplicity in this section.

Analysis visit window definitions are described in Section 7.1.1.2.1.

In the case of multiple values in an analysis visit window, data will be selected for analysis as described in Section 7.1.3.2, unless otherwise specified.

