7.4.4 Columbia Suicide Severity Rating Scale (C-SSRS)

For the C-SSRS, the number and percentage of participants with suicidal ideation, suicidal behavior, and non-suicidal self-injurious behavior as recorded on the C-SSRS scale, will be presented for each visit (refer to [Table 7-1](#) and [Table 7-2](#) for analysis visit window definitions), and overall during the treatment period.

When summarizing the lifetime history of suicidal ideation, suicidal behavior, suicidal ideation or suicidal behavior, and non-suicidal self-injurious behavior, all related data recorded on the Screening/Baseline version will be included regardless of whether the assessment date is prior to, on, or after Core Study Day 1.

When summarizing the baseline (past 6 months for suicidal ideation, or past 2 years for suicidal behavior and non-suicidal self-injurious behavior), only related data recorded on the Screening/Baseline version prior to or on Core Study Day 1 will be included.

Only data recorded on the Since Last Visit version after Core Study Day 1 will be included in the treatment period.

A shift table from Core baseline (past 6 months for suicidal ideation, or past 2 years for suicidal behavior) to each post-baseline visit and to overall during the treatment period will be provided for suicidal ideation, suicidal behavior, and no suicidal ideation or suicidal behavior. For overall, the response with the most severe suicidal ideation and suicidal behavior will be selected for a participant.

All C-SSRS data will be listed.

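### The C-SSRS shift table is anchored at Core baseline for the Titration Cohort too, so shifts in its column do not measure change since AL002 started

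*SAP*

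**What the plan says.** C-SSRS is a primary safety endpoint (protocol section 2, Table 1; SAP Table 2-1, Part 2). SAP section 7.4.4 fixes four things for it:

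- **Shift:** "A shift table from Core baseline" (looking back 6 months for ideation and 2 years for behavior), taken to every later visit and to overall.
- **Baseline records:** "only related data recorded on the Screening/Baseline version prior to or on Core Study Day 1 will be included".
- **Treatment period:** "Only data recorded on the Since Last Visit version after Core Study Day 1 will be included in the treatment period".
- **Overall:** "For overall, the response with the most severe suicidal ideation and suicidal behavior will be selected for a participant".

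None of these has an exception for the Titration Cohort. SAP section 3.2 says that Group P-TC, from which that cohort is drawn, "includes participants who were exposed only to placebo during the Core Study".

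The default in section 7.4 differs: "CFB for Titration Cohort will be based on the LTE baseline". That default gives way wherever a later section specifies something else. The SAP also provides "Table 7-2. Analysis Visit Windows for C-SSRS Assessments Based on LTE Study Day", which includes an LTE Baseline row. Section 7.4.4 cites the table for visit windows but does not use that row as the starting point of the shift.

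**The concern.** A shift table in a safety report is read as change since the drug was started. That reading is right for Group T-T, whose first AL002 dose is on Core Study Day 1, and for the placebo column. For the Titration Cohort, Core Study Day 1 is the first placebo dose, so a shift from Core baseline mixes change on placebo with change on AL002.

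The cohort has its own column in the integrated safety summaries (section 7.4.1.2) and is pooled into AL002 total (section 7.1), so the mixing reaches both. At stake is a misleading display of a primary safety endpoint. No test or error rate is involved.

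**Working it through.** The SAP attaches no figure to this display, so there is nothing to reproduce. The check compares the rules and then does short timeline arithmetic.

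**1. Does another rule re-anchor the cohort?** Elsewhere the SAP does so explicitly:

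| Display | Titration Cohort anchor | SAP section |
|---|---|---|
| Change from baseline, safety | LTE baseline | 7.4, 7.4.1.1, 7.4.1.2 |
| AE counts | Placebo and titration periods counted separately | 7.4.3.1 |
| Laboratory data | Both baselines | 7.4.5.1 |
| C-SSRS shift | Core baseline only | 7.4.4 |

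The section 7.4 default yields to specific text, and section 7.4.4 is specific. Nothing overrides the Core anchor.

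**2. How old is the baseline?** Gap in weeks = (LTE Day 1 in Core Study Days − 1) / 7. The Week 100 target in Table 7-1 is Core Day 701. Earlier entry days are assumptions; the placebo windows in Table 7-1, capped at LTE Day 1 from Week 48 onward, allow for them.

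| LTE Day 1 (Core Study Day) | Gap before first AL002 dose |
|---|---|
| 701 | 700 / 7 = 100 weeks |
| 533 (assumed) | 532 / 7 = 76 weeks |
| 365 (assumed) | 364 / 7 = 52 weeks |

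**3. How are individual histories tabulated?** For ideation in the Titration Cohort column:

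| Core baseline | On placebo | At LTE entry | On AL002 | Shift from Core baseline | Shift from LTE baseline |
|---|---|---|---|---|---|
| No | Yes | Yes | Yes | None to ideation | Ideation to ideation |
| Yes | No | No | Yes | Ideation to ideation | None to ideation |
| No | Yes, resolved | No | No | No shift at LTE visits | No shift |
| No | No | No | Yes | None to ideation | None to ideation |

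The first two rows are wrong as statements about AL002, and in opposite directions. The Core anchor is therefore not simply conservative.

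**4. Illustration with assumed counts.** Take 50 Titration Cohort participants with no ideation at Core baseline. Three develop it on placebo and still report it in the LTE; one develops it on AL002. The Core anchor shows (3 + 1) / 50 = 8% shifting to ideation, and the LTE anchor shows 1 / 50 = 2%. These counts show the mechanism only.

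**5. Can a pre-AL002 baseline be built?** Protocol section 3.2.1 makes the C-SSRS mandatory in LTE screening. Table 7-1 has Core windows at Weeks 72, 80, 96 and 100. Since Last Visit records at Weeks 80, 96 and 100 together look back to Week 72, which is 100 − 72 = 28 weeks and enough for a 6-month ideation look-back. This assumes entry near Week 100 and no missed visits.

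**The case against.** **The overall column.** A reader might infer from the treatment-period sentence that the worst response for the Titration Cohort can come from the placebo period. With entry at Core Day 701 and the last LTE target at LTE Day 393, placebo would then supply 100 of 100 + 56 = 156 weeks, or 64%. The SAP as a whole does not support this. Section 5.1 requires Group P-TC to be presented as placebo-period data and LTE-titration data separately, and section 5.2.1 carries that rule to the Non-e4/e4 Set used for integrated safety. What remains is a conflict in wording. Grouping the later data does not move the baseline, so the shift problem survives on either reading.

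**Everyone with ideation on placebo.** It is also tempting to say that every Titration Cohort participant with ideation on placebo is misclassified. That does not follow. Later C-SSRS assessments ask about the time since the last one (protocol section 6.3.11; SAP section 6.2.3), so ideation that resolved on placebo is not reported again. By-visit counts are allocated by LTE Study Day (section 7.1.1.2.1) and are sound.

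**Other capture.** Psychiatrically verified ideation or behavior must be recorded as an AE (protocol section 6.3.11). TEAEs in AL002-dosed participants start at the first AL002 dose (SAP section 6.2.2.1.2), and all C-SSRS data are listed. This limits the harm but does not correct the table.

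**A reason for the Core anchor.** The SAP describes the Screening/Baseline form, with its longer look-back, as given on Core Study Day 1. One form for all groups is a defensible motive. It does not make a baseline from before placebo treatment suitable for judging emergence on AL002.

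**Conclusion.** The point holds for the shift table. In the Titration Cohort column and AL002 total, ideation or behavior that starts on placebo and is reported again in the LTE is shown as a shift on AL002. Ideation present at Core baseline, absent at LTE entry and recurring on AL002 is shown as no shift. The baseline precedes AL002 by about 100 weeks for entry at Core Day 701, or 52 to 76 weeks under the earlier entry days assumed above.

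The number affected cannot be derived: the documents give no rate of suicidality and no rate of persistence, so any percentage-point figure would be a guess. By-visit counts, the placebo column and Group T-T stand. The treatment-period sentence needs reconciling with section 5.1 but does not by itself show that placebo events will be counted under AL002. This is a minor point, worth making because C-SSRS is a primary safety endpoint and the repair needs no new data.

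**What to change.** In SAP section 7.4.4, add for the Titration Cohort:

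- **Baseline:** the worst response in C-SSRS records up to LTE Study Day 1, including the LTE screening assessment. Use about the prior 6 months for ideation and all Core records, about 2 years, for behavior.
- **Treatment period:** Since Last Visit records after LTE Study Day 1.
- **Placebo-period C-SSRS:** reported in the placebo column only.

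Keep Core baseline for Group T-T and placebo.

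Two simpler options fall short. The existing LTE baseline rule (section 7.1.2.1) takes the last value, which looks back only to the previous assessment: about 4 weeks if that was Week 96 and the last is Week 100. A single 6-month look-back would suit ideation but not behavior, whose baseline look-back in section 7.4.4 is 2 years.

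The cost is a few sentences and one programming rule. The downside is that this baseline comes from Since Last Visit records, whereas the other groups use the Screening/Baseline form; a table footnote should say so.

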7.4.5 Laboratory Data

Laboratory data in summary tables and by-participant data listings will be presented in the International System of Units (SI units; *Système International d’Unités*).

When values are below or above a limit of quantitation, they will be listed as such, and the closest imputed value will be used for calculating summary statistics as specified in [Section 7.1.4](#).

7.4.5.2 Toxicity Grades for Laboratory Results

Participants with a toxicity grade ≥ 3 will be marked in the by-participant data listing.

7.4.6 Electrocardiogram (ECG)

Actual results and CFB values for single 12-lead ECGs (i.e., heart rate (beats/min), RR Interval (msec), QRS Duration (msec), QTcF Interval (msec)) will be summarized descriptively for each visit (refer to [Table 7-7](#) and [Table 7-8](#) for analysis visit window definitions) and separated by predose and post-infusion (refer to [Section 7.1.4.2](#) for handling of predose, post-infusion and “Not Applicable”) per each visit. In addition, shift tables from baseline to post-baseline in the Investigator’s overall interpretation of the ECG as indicated on the ECG electronic CRF will be provided for each visit. The summary will be separated by measurement time point (predose, post-infusion and “Not Applicable”) per visit. Selection of data in the event of multiple records in an analysis visit window is specified in [Section 7.1.3.2](#), separately for measurement time point (predose, post-infusion and “Not Applicable”).

For the QTcF parameter as collected on the ECG electronic CRF, the number and percentage of participants in each criterion below will be summarized separated by measurement time point (predose and post-infusion) per visit and overall during the treatment period. For overall, the record with the most severe finding will be selected for a participant.

Of the absolute QTcF interval prolongation:

- > 450 msec,
- > 480 msec,
- > 500 msec.

- Of the CFBs in QTcF interval:
 - > 30 msec,
 - > 60 msec.

The number and percentage of participants in each criterion below (Table 7-37) will be summarized separated by measurement time point (predose and post-infusion) per visit and overall during the treatment period. For overall, the record with the most severe finding will be selected for a participant.

Table 7-37 ECG Parameter Criteria

| ECG Parameter | Low Criteria | High Criteria |
|---------------|----------------|-----------------|
| Heart Rate | < 50 beats/min | > 100 beats/min |
| RR Interval | < 600 msec | ≥ 1200 msec |
| QRS Duration | < 60 msec | ≥ 120 msec |

All ECG data as collected on the ECG electronic CRF will be listed.

7.4.8 Magnetic Resonance Imaging (MRI) for ARIA-E and ARIA-H Events

Incidence of the occurrence of ARIA-E within each post-baseline visit will be summarized by radiographic severity for each visit (refer to [Table 7-12](#) and [Table 7-13](#) for analysis visit window definitions) and overall. The same incidence table will be summarized for ARIA-H. In addition to radiographic severity for ARIA-H, individual radiographic severity for microhemorrhages, leptomeningeal hemosiderosis, and macrohemorrhages for the occurrence of ARIA-H will also be summarized by visit and overall.

In the case of multiple values in the baseline analysis visit window, the rules described in the Section [7.1.3.2](#) still apply. In the case of multiple values in a post-baseline analysis visit window, the rules described in the Section [7.1.3.2](#) do not apply to this summary, but the worst-case scenario will be applied as below:

- A participant having a record indicating no ARIA-E and a different record indicating ARIA-E is considered experienced ARIA-E per visit or overall.
- A participant having experienced ARIA-E more than once per visit or overall is counted once in the number of participants with ARIA-E per visit or overall.
- The maximum severity is selected if ARIA-E was observed more than once for a participant per visit or overall post-baseline.

The same rules described above also apply to ARIA-H. In addition, the maximum severity of ARIA-H is selected for a participant per visit or overall post-baseline, and the individual radiographic severity corresponding to the selected ARIA-H will be summarized per visit or overall post-baseline.

APOE genotype, time to the first occurrence, resolution, time to resolution, and reoccurrence will be summarized for participants with ARIA-E. APOE genotype and time to the first occurrence will be summarized for participants with post-baseline ARIA-H.

The number and percentage of participants who had post-baseline ARIA-E but did not have ARIA-H any time post-baseline will be summarized. The number and percentage of participants who had ARIA-H but did not have ARIA-E any time post-baseline will be summarized. Similarly, the number and percentage of participants who had ARIA-H and ARIA-E any time post-baseline will be summarized.

Overall incidence of the occurrence of ARIA-E and ARIA-H will also be summarized by APOE genotype.

All of the MRI summaries described above will also be provided separately for participants with the following APOE genotype(s) (1) e4 carriers (including e2/e4, e3/e4 and e4/e4), and (2) non-e4 carriers (excluding e2/e4, e3/e4 and e4/e4).

For Integrated Analysis, all summaries described in this section will be provided for events across two studies as defined in Section 7.4.1.2. For LTE Analysis, only the overall summary of ARIA will be provided for events during the LTE Study.

For Integrated Analysis, the difference in proportion of participants with ARIA-E events between a slower titration rate over 48 weeks and a faster titration rate over 48 weeks will be estimated by the Cochran-Mantel-Haenszel (CMH) method adjusting for the APOE e4 status. The faster titration rate will be represented by data from the AL002 60 mg/kg treatment group during the first 48 weeks of the Core Study among participants who were on dose titration (i.e., received the first dose on or after July 22, 2021 in the Core Study) and had at least one evaluable post-baseline MRI scan. The slower titration rate will be represented by data from the first 48 weeks of the LTE Study, among Titration Cohort participants who had at least one evaluable post-baseline MRI scan in the LTE Study. Both 90% and 95% CIs for the difference in the ARIA-E events and p-value will be reported from the CMH method. The same analysis will be repeated for ARIA-H.

The statistical tests (the CMH method) of ARIA events between the slower and faster titration groups will not be performed at the first IA at the time of unblinding of the Core Study due to limited data from the LTE study at this IA, but will be performed in all analyses after the first IA.

In the Integrated Analysis, the Kaplan-Meier curves for the time to the first occurrence of ARIA-E during both the Core and LTE Studies will be plotted. For participants who experienced at least one ARIA-E, the time to the first occurrence of ARIA-E is the time from the first dose date to the onset date of the first ARIA-E occurrence. For participants who did not experience ARIA-E, the censor date will be the earlier date of the last MRI scan date, any death date, and the last dose date plus 90 days. Similarly, the Kaplan-Meier curves for the time to the first occurrence of ARIA-H will be plotted.

All MRI findings will be listed.

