## 7.2. Adverse Events of Special Interest

An AESI is a serious or nonserious AE which is of scientific and medical concern specific to a product for which ongoing monitoring and rapid reporting by the Investigator to the Sponsor should occur. AESIs are defined as the following occurrences:

- ARIA-H
  - There are 3 categories of ARIA-H which are considered separate AESI. See [Section 7.11](#) for additional details.
- ARIA-E
- ██████████

For AESI, the most appropriate diagnosis should be recorded on the AE eCRF and reported to the Sponsor immediately (ie, no more than 24 hours after learning of the event) as an AESI, regardless of whether the AESI is deemed to have a possible relationship to the study drug or not.

Management of ARIA are described in [Section 7.11](#). ██████████ should be managed by an ophthalmologist and the Medical Monitor.

The reporting of an AESI will trigger an auto notification email alert from electronic data capture (EDC) to the Medical Monitor.

In the event that EDC is not functioning, the Investigator should utilize the back-up paper process described below for SAE reporting and clearly indicate if the event is nonserious or serious, and related or not related to study drug in the opinion of the Investigator, and that the event is assessed as an AESI.

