## 7.11. Amyloid-Related Imaging Abnormalities

Among the brain abnormalities detected on MRI are ARIA, which are believed to reflect leakage of proteinaceous fluid or other blood products into the leptomeninges or brain parenchyma. The term ARIA was originally coined to describe specific brain abnormalities seen on MRI in anti-amyloid clinical trials. Although MRI findings potentially caused by AL002 may or may not be related to disruption/mobilization of, or a reaction to, amyloid species in the brain parenchyma or vasculature, the term ARIA will be used in this protocol to describe such findings until the biological mechanism is better understood. Specifically, according to the convention developed to describe ARIA occurring in clinical trials of anti-amyloid immunotherapies, ARIA-E will refer to MRI findings of vasogenic edema and leptomeningeal/sulcal effusion, and ARIA-H will refer to MRI findings of cerebral microhemorrhages, leptomeningeal hemosiderosis (also known as superficial siderosis of the CNS), and cerebral macrohemorrhages.

For the purpose of this protocol, 4 categories of ARIA will be tracked (see [Section 7.6.4](#) for recording of AESIs of ARIA). These categories are ARIA-E, ARIA-H cerebral microhemorrhages, ARIA-H leptomeningeal hemosiderosis, and ARIA-H cerebral macrohemorrhages. Symptoms associated with ARIA-H and ARIA-E will be captured as separate AEs on the AE eCRF and linked to the applicable ARIA AE line number. All clinical signs and symptoms that are identified as associated with an ARIA finding will be entered as separate AEs on the AE eCRF. Based on evaluation of the participant for signs and symptoms, and review of safety findings by the Sponsor that possibly indicates the presence of ARIA, the Sponsor may request an unscheduled MRI be obtained.

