**Table 7: ARIA-E and ARIA-H Radiographic Severity Scales**

ARIA-E Characterization:	Severity/Grade		
<5 cm monofocal	Mild (Grade 1)		
<5 cm multifocal	Mild+ (Grade 2)		
5-10 cm monofocal	Moderate (Grade 3)		
5-10 cm multifocal	Moderate+ (Grade 4)		
>10 cm monofocal/multifocal	Severe (Grade 5)		
Incident ARIA-H:	Mild	Moderate	Severe
Microhemorrhages	1-4	5-9	10 or more
Areas of leptomeningeal hemosiderosis	NA	1	2 or more
Macrohemorrhages	NA	NA	1 or more

ARIA-E=amyloid-related imaging abnormalities-edema; ARIA-H=amyloid-related imaging abnormalities-hemosiderin deposits; NA=not applicable.

Overall, ARIA-H radiographic severity is defined as the worst individual radiographic severity for microhemorrhages, leptomeningeal hemosiderosis or macrohemorrhages (eg, if there are 4 incident microhemorrhages, 1 incident areas of leptomeningeal hemosiderosis, and no macrohemorrhages, then ARIA-H is rated as “Moderate”).

ARIA-H findings very rarely resolve radiographically; it is more typical for ARIA-H findings to stabilize radiographically. Radiographic stabilization of an ARIA-H finding is defined as when a follow-up MRI scan shows no increase in number/size/extent of previously seen cerebral microhemorrhages, leptomeningeal hemosiderosis, and cerebral macrohemorrhages.

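### ARIA-H component severities are read from one record chosen on overall grade, with no tie-break, so the component summary in SAP 7.4.8 can understate siderosis or, in a tie between Severe scans, a macrohemorrhage

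*SAP*

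**What the plan says.** SAP 7.4.8 plans ARIA-H incidence by radiographic severity and adds that "individual radiographic severity for microhemorrhages, leptomeningeal hemosiderosis, and macrohemorrhages for the occurrence of ARIA-H will also be summarized by visit and overall". Where a post-baseline window holds several records, the general selection rules of SAP 7.1.3.2 "do not apply to this summary, but the worst-case scenario will be applied as below". For ARIA-H, "the maximum severity of ARIA-H is selected for a participant per visit or overall post-baseline", and then "the individual radiographic severity corresponding to the selected ARIA-H will be summarized per visit or overall post-baseline". Nothing says which record is used when two share the highest overall grade.

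Protocol 7.11 with Table 7 defines the grades: "Overall, ARIA-H radiographic severity is defined as the worst individual radiographic severity for microhemorrhages, leptomeningeal hemosiderosis or macrohemorrhages". Microhemorrhages are Mild for 1–4, Moderate for 5–9 and Severe for 10 or more. One area of siderosis is Moderate and two or more are Severe. Under the columns Mild, Moderate and Severe, the last row reads "Macrohemorrhages NA NA 1 or more", so any macrohemorrhage is Severe.

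The protocol keeps the components apart. Section 7.2 states "There are 3 categories of ARIA-H which are considered separate AESI", and section 7.11 states "For the purpose of this protocol, 4 categories of ARIA will be tracked", meaning ARIA-E and the three ARIA-H types.

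SAP 6.2.7.2 takes new ARIA-H severity in the LTE, overall and by component, from the Brain MRI Worksheet. Table 7 labels the counts as incident. Neither says which earlier scan is the reference. By-visit and overall ARIA summaries are planned for the Integrated Analysis; the LTE Analysis gets the overall summary only.

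**The concern.** The section announces a worst-case approach and applies it to the overall ARIA-H grade, but not to the components. Their grades come from whichever record won on the overall grade. Since that grade is a maximum of three, the winning record can be worst for one component and blank for another. The reported component grade can equal the participant's true worst grade or fall below it; it cannot exceed it.

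MRI abnormalities are a Part 2 primary safety endpoint in SAP Table 2-1, and the component summary in 7.4.8 is the only planned tabulation of the Table 7 grade by component. Adverse event tables use CTCAE severity instead (Protocol 7.5.1). The participants exposed are those with several abnormal scans and mixed findings. Protocol 7.11.2 has new ARIA-H rescanned every 4–6 weeks until stable, so repeat scans are built in for them. In the Integrated Analysis, the overall column could show fewer participants with a component than the by-visit columns of the same table.

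**Working it through.** The plan gives no figure to reproduce; the check is on what the selection rule can do.

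**1. Possible scans.** From Table 7, microhemorrhage has 4 levels (none, Mild, Moderate, Severe), siderosis 3 (none, Moderate, Severe) and macrohemorrhage 2 (none, Severe). That gives 4 × 3 × 2 − 1 = 23 scans with some ARIA-H, and 23 × 23 = 529 ordered pairs. The counts below show what is possible, not how often it occurs.

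**2. Rule applied.** Keep the scan with the higher overall grade, read the components from it, and compare with each component's own maximum over both scans.

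**3. Unequal overall grades, any pair.**
- Macrohemorrhage lost: 0 of 529. Its scan is already at the top grade, so no other scan can outrank it.
- Siderosis lost: 3 Moderate scans with one siderosis area × 5 Severe scans without siderosis = 15 distinct pairs, or 30 ordered pairs.
- Example: scan A has one siderosis area (overall Moderate); scan B has 10 new microhemorrhages (overall Severe). B is selected, so siderosis is reported as none against a true worst grade of Moderate.

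**4. Tied overall grades, any pair, least favorable choice.**
- Macrohemorrhage can be lost in 12 × 6 × 2 = 144 ordered pairs (12 Severe scans with a macrohemorrhage, 6 without).
- Siderosis can be lost in 136 ordered pairs: 5 × 13 × 2 = 130 between Severe scans and 3 × 1 × 2 = 6 between Moderate scans.

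**5. Cumulative grading.** If findings carry forward, no component grade falls from the first scan to the second, and 156 pairs remain.
- Unequal grades: nothing is lost.
- Ties: a macrohemorrhage is lost in 15 pairs and siderosis in 25, if the earlier scan is used.
- Example: scan 1 has 10 microhemorrhages (Severe); scan 2 has the same 10 plus one macrohemorrhage (Severe). Using scan 1 reports 0 macrohemorrhages against 1.

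**6. Where two scans compete.** In the overall table, all post-baseline scans compete. In a by-visit cell, only scans in the same window do. LTE MRI windows in SAP Table 7-13 include [86, 141], which is 141 − 86 + 1 = 56 days, and [254, 337], which is 84 days. Core windows in Table 7-12 reach [254, 421], which is 168 days. With rescans every 28–42 days, one window can hold more than one scan.

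**7. Size of one lost case.** SAP 3.5 expects 176–198 participants. Assuming an equal split over four groups (the documents give no LTE group sizes), a group has 176/4 = 44 to 198/4 = 49.5 participants, so one lost case is 1/49.5 = 2.0 to 1/44 = 2.3 percentage points.

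**8. After the fix.** With each component's own maximum, nothing is lost in any of the 529 pairs. The overall grade is unchanged, because it is the maximum of the same components.

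**The case against.** Reporting the components of a participant's worst ARIA-H record is a coherent description of that event. In the tie example, the worst-case principle itself points to the scan with the macrohemorrhage, so a careful programmer would lose nothing. The two routes to loss also lean on different worksheet readings: persistence produces ties mainly if grading is cumulative, while loss without a tie needs grading of findings new since the prior scan. Most ties from persistence carry the same components and lose nothing. Protocol Table 8 has treatment discontinued after Severe ARIA-H, which should limit runs of evolving Severe scans.

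Much of this stands, and it rules out three stronger inferences.
- A reader might infer that a worse scan can displace a macrohemorrhage. It cannot, because any macrohemorrhage is already Severe.
- A reader might infer that harmful ties will be common. The documents support repeat scans, but not a frequency of Severe scans that differ in their components.
- A reader might infer that the primary safety tables as a whole are compromised. AESI counts come from the adverse event form, not from this record selection. Findings in other windows stay in the Integrated by-visit tables, and all MRI findings are listed.

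What does not stand is that the worst-case principle settles the matter. If one Severe scan has a macrohemorrhage and no siderosis, and another has two new siderosis areas and no macrohemorrhage, either choice drops one component. Under new-since-prior grading, the loss of a single siderosis area follows from the rule as written, with no tie involved.

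**Conclusion.** The component rule conflicts with the worst-case principle of its own section and should be changed. The effect is one-sided and confined to the ARIA-H component summary: the overall table, and a by-visit cell when one window holds several scans. One siderosis area is dropped without a tie only if the worksheet grades findings new since the prior scan, which the documents leave open. With a tie, siderosis or a macrohemorrhage can be dropped under either grading.

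Exposure is greatest in the LTE Analysis, which has no by-visit table to show the missing finding. The frequency cannot be estimated; the 2.0–2.3 percentage points per lost case rests on the assumed equal split. Integrated ARIA definitions follow the Core Study SAP, which is not among the documents, so consistency with Core reporting cannot be judged.

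**What to change.** In SAP 7.4.8, replace the clause that reads the components from the selected ARIA-H record with: *for each of microhemorrhages, leptomeningeal hemosiderosis and macrohemorrhages, the maximum severity across all post-baseline scans in the visit window (or overall), selected independently of the scan that gives the maximum overall ARIA-H severity*. Leave the rule for overall ARIA-H severity as it is.

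This works under either worksheet reading and makes a tie-break unnecessary. It costs one sentence in the SAP and a small programming change, with no new data.
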